Pre-screening phone interviews may be performed when appropriate to assist in identifying individuals who are likely to meet all eligibility criteria. Pre-screening interview questions will collect information about a person's demographics, health history, and any active skin conditions they may have, and will walk through the trial's inclusion and exclusion criteria. Participants will be advised of exclusionary medications and the required washout period, and that they should consult their doctor before stopping any medications before the screening visit. We may also ask for photographs to be sent to the study team via encrypted email or by text (participant's preference) to allow dermatologists to perform an initial assessment of skin condition severity to prevent unnecessary screening visits from participants who clearly would not meet inclusion criteria.

Our recruitment and pre-screening efforts will be intentionally broad in order to bring in individuals with DS with any *potentially* immune-driven skin condition for a screening visit. In our experience with the HTP, many individuals self-report issues like "dry" or "rough" skin, or medical records will indicate non-specific diagnoses like "boils." However, in many cases a dermatologist was never consulted for a proper diagnosis. Thus, we anticipate that some individuals will qualify for the trial without otherwise having known that they actually have AD or HS, for instance. Based on our experience in dermatology clinical trials, we estimate that between 25-50% of individuals recruited and brought in for a screening visit will end up "failing" and will not qualify for or be willing to comply with the trial criteria. We also estimate that up to 15% of participants will be lost over the course of the ~5-month study timeline due to attrition. These considerations lead us to plan to recruit 77 individuals for screening in order to enroll 47 individuals, of whom 40 will complete the study. However, to account for additional unforeseen screen fails and attrition, we are asking to screen up to 100 participants.

Informed Consent, Assent, LARs, and Consent Procedures.

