Each visit will entail a physical exam, collection of vital signs, recording and monitoring of adverse events (AEs, see below), and a blood draw for the same battery of safety monitoring labs described in the screening procedures above. A follow-up ECG will be performed for all participants at the 4-week visit and as needed based upon concomitant medications at the study doctor's discretion. An audiogram will be performed before beginning treatment and after 15-16 weeks of treatment, to ensure Tofacitinib has not impacted hearing. A recent audiogram performed within the past 12 months for clinical reasons can be provided or accessed by the study team will be accepted, given that the appropriate elements were evaluated and no change in hearing status is anticipated. A negative Quantiferon Gold, Quantiferon Gold Plus or Quantiferon Gold HA and chest x-ray that have been obtained for clinical reasons within the past 12 months will be accepted for screening purposes if no change in TB status is anticipated. Participants will receive a tuberculosis screen at least every 12 months while in the study. Outside laboratory results will be accepted at the study doctor's discretion (Figure 6). Every effort will be made to have the same study doctor meet with a participant at each visit to minimize interrater bias. Skin conditions will be formally assessed at screening, baseline, 8, and 16 weeks by a dermatologist using standard and accepted metrics, such as: Investigator's Global Assessment (IGA) and Dermatology Life Quality Index (DLQI) for all skin conditions, Eczema Area and Severity Index (EASI) for AD, Severity of Alopecia Tool (SALT) for AA, Modified Sartorius Score (MSS) for HS, Psoriasis Area and Severity Index (PASI) for psoriasis, and Vitiligo Extent Tensity Index (VETI) for vitiligo. Note that the Hidradenitis Suppurativa – Physician's Global Assessment (HS-PGA) will be used to determine eligibility for participants with HS at screening and for EA qualification, while the MSS will be ongoing. Photographs will also be taken of the affected area(s) at the time of these assessments for additional validation of skin condition and visual, qualitative indicators of improvement or progression. Photographs may be taken at other safety visits to document response to treatment at the study doctor's discretion. Open-source online scoring calculators may be used to calculate skin condition severity, provided no PHI is entered. Participants in the Extension Arm will also have a formal skin assessment at 28 and 40 weeks.

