Method: This number is based on published safety data for Tofacitinib for the treatment of rheumatoid arthritis in the general population, which indicates a rate of 9.4 SAEs per 100 patient years. Given that our trial aims to enroll 47 participants for 16 weeks of treatment (though we anticipate up to seven participants would be lost to attrition at various times during the treatment course) for a maximum total of 14.5 patient years of treatment, a comparable number of SAEs is 1.36.

Specific Aim 2. To determine the impact of JAK inhibition on the immune dysregulation caused by trisomy 21.

The overall goal of our data analysis plan in this Aim is to define which immune processes dysregulated by T21 can be normalized by Tofacitinib treatment, i.e. returned to values observed in typical people. Importantly, data shown in this proposal demonstrate that we have already defined the directionality and average magnitude of the change between people with and without T21. For example, we determined that IFN scores are significantly higher in people with DS (*Figure 3C*) and expect that Tofacitinib will reduce these values. Whereas some of the features dysregulated by T21 may be normalized by Tofacitinib treatment, others may not, and this will provide an important mechanistic insight to understand the molecular underpinnings of immune dysregulation in DS. Accordingly, the endpoints associated with this Specific Aim focus on effects of Tofacitinib (16 weeks of treatment) on four classes of molecular markers of immune dysregulation:

Primary Endpoint: Change in IFN scores in the transcriptome of white blood cells.

Endpoint Definition: Statistically significant reduction in average IFN scores between baseline and 16 weeks as defined by a two-sided, paired Student's t-test.

Method: To determine the impact of Tofacitinib on IFN scores, a two-sided, paired Student's t-test will be used to compare baseline and 16 weeks of treatment for participants with good compliance with the study drug (2 or fewer missed pills) and without a confounding reported adverse event in the 7 days prior to the Visit 7 endpoint. With 40 participants, we have 80% power to detect an effect size of 0.45 with a p-value <0.05, as calculated by G*Power software.

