Endpoint Definition: A statistically significant *percentage reduction* in one or more metrics of skin pathology, including: a) IGA values, b) DLQI values, and/or c) disease-specific scores between baseline and 16 weeks as defined by a two-sided, paired Student's t-test.

Method: The first endpoint for this Specific Aim will be to monitor changes in the Investigator's Global Assessment (IGA), which is a well-established, disease-agnostic measurement of skin disease severity that employs a continuous visual analog scale and has good test-retest reliability. A second disease-agnostic secondary endpoint will be the Dermatology Life Quality Index (DLQI), a patient-reported outcome that is commonly used in dermatology trials. The third secondary endpoint for this study is a percentage reduction in the disease-specific measurements used to monitor each skin condition. We will employ Eczema Area and Severity Index (EASI) for AD, Severity of Alopecia Tool (SALT) for AA, Modified Sartorius Score (MSS) for HS, Psoriasis Area and Severity Index (PASI) for psoriasis, and Vitiligo Extent Tensity Index (VETI) for vitiligo. By focusing on a *percentage reduction* in disease-specific scores, we will be able to compare values from participants with different conditions. In every case (IGA, DLQI or disease-specific scores) we will define whether the percentage reduction reaches significance using a two-sided, paired Student's t-test comparing baseline and 16 weeks of treatment. In every case, for 40 individuals, we have 80% power to detect an effect size of 0.45 with a p-value less than 0.05, as calculated by G*Power software. Finally, although we will be analyzing changes between baseline and 16 weeks, data will be also gathered at the intermediate time point of eight weeks for research purposes.

Specific Aim 4. To characterize the impact of JAK inhibition on cognition and quality of life in Down syndrome.

Tertiary Endpoint: Change in any one or more of the cognitive assessments performed.

Endpoint Definition: a statistically significant improvement in any one of the cognitive measures employed between baseline and 16 weeks as defined by a Wilcoxon signed-rank test with FDR correction or a two-sided, paired Student's t-test, as appropriate.

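### The skin endpoint test uses only participants with a week-16 score (about 40 of 47 planned) and leaves out the scheduled week-8 scores, so the mean improvement can be overstated if loss follows poor response.

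*Combined protocol and SAP*

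**What the plan says.** Section VII, Specific Aim 3 (Method), covers the IGA, the DLQI and the disease-specific scores. Each is judged by a "two-sided, paired Student's t-test comparing baseline and 16 weeks of treatment". The power statement is "In every case, for 40 individuals, we have 80% power to detect an effect size of 0.45 with a p-value less than 0.05".

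Section IV.C, Recruitment and Pre-Screening, shows where the 40 comes from: "plan to recruit 77 individuals for screening in order to enroll 47 individuals, of whom 40 will complete the study". The same section gives the loss rate: "We also estimate that up to 15% of participants will be lost over the course of the ~5-month study timeline due to attrition". On timing, the Specific Aim 1 method in section VII says "we anticipate up to seven participants would be lost to attrition at various times during the treatment course".

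On the visit schedule, section IV.C, Study Visits and Activities, says: "Skin conditions will be formally assessed at screening, baseline, 8, and 16 weeks by a dermatologist". The Specific Aim 3 method then keeps the intermediate scores out of the endpoint: "data will be also gathered at the intermediate time point of eight weeks for research purposes".

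The documents give no analysis set for the skin endpoints, no rule for a missing week-16 score and no sensitivity analysis for participants who lack one. The only repeated-measures analysis is the secondary one on age and sex, and the plan states that it cannot change whether an endpoint is met.

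**The concern.** A paired t-test needs both scores. A participant who leaves after week 8 therefore contributes nothing to the skin result, even though a dermatologist has recorded a response at week 8. The mean among those who reach week 16 estimates the mean in all treated participants only if loss is unrelated to response.

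The protocol contains routes by which loss could be related to it. Participants may leave for any reason, and may be removed for an adverse event, an abnormal laboratory finding or 15% missed doses (Participant Discontinuation and Trial Stopping). Extension Arm candidates are first identified at week 8. For atopic dermatitis, psoriasis and most alopecia areata, qualification needs some improvement by then, so participants without early benefit may have less reason to stay. The trial is open-label with one arm, so no control group can offset selective loss.

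Section IV.C, Research Methods for Specific Aim 3, calls skin improvement the main secondary endpoint. What is at stake is mostly the size of the improvement, which a follow-up trial would be designed on.

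**Working it through.** **1. The plan's own figures.** Inputs: n = 40, standardised effect 0.45, two-sided alpha 0.05. For a paired t-test with 39 degrees of freedom and noncentrality 0.45 × √40 = 2.85, exact power is 79.3%, which agrees with the stated 80%. Attrition: 47 × 0.85 = 39.95, so 40; and 7/47 = 14.9%. The power statement therefore rests on the 40 who complete, not on the 47 treated.

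**2. Bounds on the mean.** Let M be the mean improvement in the 40, and f × M the mean in the 7 without a week-16 score. The documents do not give f, so it is an assumption. The all-treated mean is M × (40 + 7f)/47.

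| f | All-treated mean | 40-participant mean too high by |
|---|---|---|
| 1 (same response) | 1.00 M | 0% |
| 0.5 | 0.926 M | 8% |
| 0 (no benefit) | 0.851 M | 17.5% |
| −0.5 | 0.777 M | 29% |
| −1 (worsened as much as the others improved) | 0.702 M | 42% |

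At f = 0 a reported 40% corresponds to 40 × 40/47 = 34% in all treated.

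**3. Effect on the p-value.** Set the SD in the 40 to 1 and the mean to d, and give each of the 7 the value f × d. Then the mean is m = d(40 + 7f)/47, the variance is [39 + 40d² + 7(fd)² − 47m²]/46, and t = m√47/SD.

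| Result in the 40 | f = 0 | f = −0.5 | f = −1 |
|---|---|---|---|
| d = 0.45, p = 0.0070 | 0.0073 | 0.015 | 0.031 |
| d = 0.32, p = 0.050 | 0.050 | 0.076 | 0.112 |

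Counting the seven as unchanged leaves significance almost where it was. Only a borderline result combined with actual worsening crosses 0.05.

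**4. What the week-8 scores can recover.** The documents give no SD of change, no week-8 to week-16 correlation and no dropout mechanism, so all three are assumed. With two visits and loss after week 8, the likelihood estimate of the week-16 mean is a + b × (mean week-8 change in everyone scored at week 8). Here a and b come from regressing week-16 on week-8 change among those with both. Simulated trials had 47 participants, 7 of them lost, a true week-16 reduction of 40%, SD 30 to 35 and correlation 0.5 to 0.7:

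| Loss | Paired t-test set | Likelihood estimate with week 8 |
|---|---|---|
| Random | 40% | 40% |
| Follows poor week-8 response, all scored at week 8 | 41.6–44.5% | 40% |
| Same, but 3 of the 7 leave before week 8 | as in the row above | 40.7–42.1% |
| The 7 have zero week-16 change, not foreshadowed at week 8 (all-treated mean 34%) | about 40% | 39.9–40.0% |

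Widening the assumptions (SD 20 to 40, correlation 0.3 to 0.85, moderate or strong dependence of loss on response) gives 40.5% to about 45% for the paired t-test set. The gain in standard error is about 0 to 4%.

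**5. What a no-change rule does.** In standardised simulations with a true change of 0.45, counting the seven as unchanged gives 0.38 under random loss. Under loss that follows poor week-8 response it gives 0.48 to 0.52, against 0.56 to 0.61 in the 40. It is useful as a sensitivity analysis but is not an unbiased main estimate.

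**The case against.** Several points on the other side stand.

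- **Direction.** A reader might infer that the result will be biased upward. The documents do not show that. Some losses need have nothing to do with skin response, such as missed visits or COVID-19. Long-standing alopecia areata is invited to the Extension Arm without improvement, and hidradenitis suppurativa and vitiligo may be at the study doctor's discretion. Stopping drug does not by itself end study participation. The bias is conditional.
- **Size.** A reader might infer that a mixed model would recover the 17.5%. It would not. That figure takes the seven as having no benefit, whereas the model predicts their week-16 value from week 8. If week 8 does not foreshadow the failure, the model changes nothing (last row of step 4).
- **Timing.** Losses are expected throughout treatment. Anyone lost before week 8 has no later score for the model to use.
- **Success criterion.** The endpoint is defined by significance, which hardly changes when the lost participants are counted as unchanged.
- **Precision.** A gain of 0 to 4% would not justify the change on its own.
- **Small groups.** Forty participants over five conditions average 8 each, so a repeated-measures model by condition would add little. A pooled model also assumes a common week-8 to week-16 relationship, although section VI expects atopic dermatitis to respond faster than vitiligo.

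What does not stand is the view that the change is only a matter of preference. The plan expects up to 15% loss, gives no rule for it, and sets aside scores that it has already scheduled.

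**Conclusion.** The point holds in conditional form. The skin test uses only participants with a week-16 score, about 40 of 47 planned. This follows from the paired test, the stated 40 and the absence of a missing-data rule; the plan does not itself name a completer set. Seven is a planning figure for losses, not a cap.

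If loss is related to poor response, the mean improvement can be overstated: about 41.6% to 44.5% against a true 40% under the assumed SDs and correlations, and 17.5% in relative terms if all seven had no benefit. If loss is random there is no bias. The p-value is little affected unless the lost participants worsened and the result was borderline. A reader should not conclude that the significance result is in doubt in general. Nor are the week-8 scores unused in the trial: they inform Extension Arm qualification and are left out only of the endpoint analysis.

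The change is worth making because the effect size is the figure others will use and the data are already scheduled.

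**What to change.** 1. For the pooled percentage change in IGA and in disease-specific score, define the analysis set as all treated participants with a baseline score and at least one later score. Analyse weeks 8 and 16 together in a mixed model for repeated measures, and test the week-16 mean.
2. Add a sensitivity analysis on all treated participants that counts those without a week-16 score as unchanged from baseline. The model cannot help those lost before week 8, or those whose later outcome week 8 does not predict.
3. Keep the paired t-test in participants with both scores as a further sensitivity analysis.
4. Reconcile the DLQI schedule within section IV.C, Study Visits and Activities. One paragraph includes the DLQI among the metrics for the formal skin assessments, which take place at week 8 as well; a later one lists baseline, week 16 and week 40 only. Whatever the answer, apply at least the no-change sensitivity analysis to the DLQI.

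The cost is a wording change and a little more analysis; no new visits or measurements are needed. The main model relies on loss being random given the week-8 score, which is why item 2 is needed alongside it.
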